responders involved in the opioid and heroin epidemic (law enforcement, firefighters, and emergency medical system personnel) compared to baseline measures and reduced stress as measured by salivary cortisol.

Specific aim #2: Determine delivery and acceptability among first responders in Appalachia. MBRT is relatively novel in this population and to our knowledge has never been applied to a broader first responder community outside law enforcement and not to our knowledge in Appalachia.

Specific aim #3: Evaluate the delivery of MBRT in an intensive 2.5 day setting with follow up remotely with an online communication method such as Skype, FaceTime, or Zoom.

Hypotheses: We hypothesize the following based on previous research:

- 1. MBRT will improve self-reported measures over the 2.5-day intensive intervention with a remote, virtual booster intervention 4 weeks after the 2.5-day initial intervention relative to baseline: a) Mindfulness and resilience, b) Physical and mental health, c) Stress and burnout, d) Emotional functioning, and e) Family functioning, f) Sense-making and decision-making.
- Pre- to post-MBRT changes in mindfulness, physical health, mental health, and stress would predict post-MBRT salivary cortisol, while controlling for pre-MBRT salivary cortisol

Design

1. Fully describe all procedures to be performed in sequential order in outline format.

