judgmental.³ The Brief Resilience Scale is a 6-item scale designed to assess the ability to recover from stress using a 5 point Likert scale.⁴ To measure health outcomes, the Patient Reported Outcomes Measurement Information System (PROMIS®) designed to improve selfreported In this study, we plan to use short form versions of several PROMIS domains to assess health outcomes. The Global Health Short-Form is a 10-item instrument representing multiple domains that can be scored into a Global Physical Health (GPH) component and Global Mental Health (GMH) component. Additionally, we assessed Anger (8 items), Fatigue (4 items), Sleep Disturbance (4 items), and Pain Interference (4 items). All items are rated on a 5-point Likert-type scale using various endpoints.⁵ Stress and burnout will be measured with the 4-item Perceived Stress Scale-4 (PSS-4) to assess perceived stress in life situations.⁶ The Police Stress Questionnaire (PSQ) is a 40-item questionnaire consisting of two subscales measuring operational stressors (20 job content items) and organizational stressors (20 job context items) on a seven-point Likert-type scale, ranging from 1 (no stress at all) to 7 (a lot of stress), and higher scores indicate greater stress. Nearly all the questions could be applicable to all first responder groups. ⁷ The Oldenburg Burnout Inventory (OLBI) is a 16-item measure of burnout with two dimensions: exhaustion and disengagement.8 The Emotional Intelligence Scale (EIS; Schutte et al. 1998) is a 33-item scale of emotional intelligence. Items are rated on a 5-point Likert scale ranging from 1 (strongly disagree) to 5 (strongly agree), and three items are reverse scored. All items are summed to create a total score, and higher scores indicate greater emotional intelligence. 9 The Difficulties in Emotion Regulation Scale (DERS) is a 36-item measure that assesses clinically relevant difficulties in emotion regulation. Items are scored on six scales: lack of emotional awareness (6 items), lack of emotional clarity (5 items), difficulties controlling impulsive behaviors when distressed (6 items), difficulties engaging in goal-directed behavior when distressed (5 items), non-acceptance of negative emotional responses (6 items), and limited access to effective emotion regulation strategies (8 items).10 Family functioning will be measured through the Family Assessment Device (FAD), a 60-item measure.11 The FAD consists of six subscales and a seventh subscale (general family functioning: GFF) incorporates items from the six subscales. In this study we plan to use the 12-item GFF scale, which can be used as an indicator reflecting global family functioning. 12 Salivary cortisol is a biologic marker for stress and is a measure of the hypothalamic-pituitary-adrenal axis (HPA axis). One of the characteristics of the HPA axis is the strong circadian rhythm and the cortisol awakening response (CAR). Salivary cortisol levels are highest in the morning after awakening, and decline throughout the day and lowest around midnight, to rise again in the early morning hours. A distinct characteristic of the HPA axis is the cortisol awakening response (CAR). 13 The CAR is characterized by a sharp rise (between 50 and 75%) of cortisol levels within the first 30 minutes after awakening. 14 Repeated measurement of free cortisol levels within the 60 minutes after awakening in the morning is considered a stable and reliable biological marker of adrenocortical activity.15 We plan to collect approximately 2-3 ml of saliva at 0, 30, and 45 minutes after awakening in the morning at times 0,1,2, and 3 as described above. To examine changes in our measures during the course of MBRT, we plan to use a multilevel modeling approach with restricted maximum likelihood estimation (REML) to examine linear change over time as a fixed effect. We used REML because our data collection resulted in varying sample sizes for our measures, allowing for more accurate estimates with small sample sizes and missing data that are missing at random or completely at random ^{16,17} To test whether changes in mindfulness, emotional intelligence, and difficulties with emotion regulation (i.e., process variables) preceded changes in mental health, physical health, stress, pain interference, anger, fatigue, sleep disturbance, burnout, resilience, and family functioning (i.e., outcome variables), using the

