
multilevel modeling approach, we plan to examine which variables significantly change from time 0 to time 1, from time 1 to time 2, from time 2 to time 3, and from time 0 to time 2 and time 3. To analyze the CAR, plan to use multilevel modeling with REML examining the main effects of phase of measurement (pre, post as above) and time after waking (0, 30, 45 minutes), as well as the interaction between the main effects. We also plan to investigate the association between the cortisol response patterns and change in mindfulness (FFMQ), stress (PSS-4), physical health, and mental health. For that purpose, we plan to analyze the area under the curve with respect to increase (AUCI) to analyze the linear relationship between each independent variable and cortisol awakening levels. Cortisol levels will be transformed into a single value by calculating the AUCI for each assessment day (1 pre and 1 post). These variables will be used in a hierarchical linear regression with pre-AUCI entered in step 1, and change in stress, physical health, mental health, and mindfulness entered in step 2, to predict post-AUCI. Alpha will be set at .05 for all analyses. The PI will be responsible for recruitment of subjects and coordinating with researchers and staff at WVU for analysis and will help oversee the implementation of the intervention. The co-PI will also assist with overseeing the intervention as well as scheduling follow-up, particularly in the Huntington community and will assist in analysis and in evaluation of difficulties. Such difficulties may include scheduling difficulties for follow-up after the intensive intervention, subject drop-out, and sustaining local resources to assist the subjects.

2. Discuss probability of group assignment to experimental and control groups.

Participants will serve as their own controls so they will participate in both the control group and the interventional group.

3. Inclusionary Criteria

Participants must meet the following inclusionary criteria to be eligible for the study: Be employed as a law enforcement official, firefighter, or emergency medical services technician or supervisor from Cabell, Kanawha, or Putnam Counties.

4. Exclusionary Criteria

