Exclusionary criteria include 1) at high risk for suicide, 2) a current psychotic disorder or significant co-morbid diagnosis (e.g., Schizophrenia, Schizoaffective Disorder, etc.), 3) high score on of 3 screening tools (PSS-4, PSQ, and DERS) with follow-on questioning which would indicate referral to a mental health practitioner, 4) primary substance use disorder.

If a patient becomes suicidal during the course of their participation in the study they will be evaluated and provided immediate intervention to ensure their safety and stabilization.

- 5. Does the research involve more than minimal risk to participants?
- 6. Describe the provisions to monitor the data to ensure the safety of participants

(data and safety monitoring plan).

a. Who will monitor the data?

All survey data will be monitored by the Principal Investigators.

b. What "data" will be monitored?

The study is composed of three general sets measures that will be monitored: primary outcome measures, secondary outcome measures, and mediating measures.

Primary Outcome Measures

The following self-assessment tools will be used:

The Brief Resilience Scale is a 6-item scale designed to assess the ability to recover from stress using a 5-point Likert scale.⁴

To measure health outcomes, the Patient Reported Outcomes Measurement Information System (PROMIS®) designed to improve self-reported in this study, we plan to use short form versions of several PROMIS domains to assess health outcomes. The Global Health Short-Form is a 10-item instrument representing multiple domains that can be scored into a Global Physical Health (GPH) component and Global Mental Health (GMH) component. Additionally, we will assess Anger (8 items), Fatigue (4 items), Sleep Disturbance (4 items), and Pain Interference (4 items). All items are rated on a 5-point Likert-type scale using various endpoints.⁵

Stress and burnout will be measured with the 4-item Perceived Stress Scale-4 (PSS-4) to assess perceived stress in life situations.⁶

The Police Stress Questionnaire (PSQ) is a 40-item questionnaire consisting of two subscales measuring operational stressors (20 job content items) and organizational stressors (20 job context items) on a seven-point Likert-type scale, ranging from 1 (no stress at all) to 7 (a lot of stress), and higher scores indicate greater stress. Nearly all the questions could be applicable to all first responder groups.⁷

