Yes.

12. Include a literature review and explain the scientific rationale for the study.

Mindfulness-based resilience training (MBRT) is based on mindfulness-based stress reduction (MBSR) first introduced at the University of Massachusetts School of Medicine in 1979 by Jon Kabat-Zinn. The original 8-week program was designed to teach participants to use their innate inner resources to enhance awareness to the present moment experience, primarily through experiential, non-cognitive learning about the mind's capacity to create stories which may or may not correlate with what is really happening in the present. This program has been described in detail and studied rigorously in many contexts of physical and mental health.¹⁸ MBRT builds on the original 8-week course structure of MBSR and is designed to train participants in a number of experiential exercises evoking qualities of mindfulness: mental focus, sustained attention and personal and situational awareness. These exercises include versions of the body scan (body awareness exercise), sitting meditation, mindful movement, walking meditation, eating meditation, mindful martial arts exercises and other elements of MBSR. These studies demonstrated effectiveness across a wide range of measures of physical and mental health.^{1,19} Our plan is to use identical measures as the original pilot study¹ but modify the delivery after empiric unpublished observations by one of the authors, [name], that a shorter but intensive intervention was more likely to be effective than an 8-week course with a 4-week post-intervention follow-up. This study therefore builds on the demonstrated success of prior MBRT interventions with three changes: Cultural venue (Appalachia as opposed to the Pacific Northwest), includes fire and EMS in addition to law enforcement, and is presented in a 2.5-day intensive intervention with a 4-week remote follow-up (booster) and a 3-month postintensive intervention evaluation.

HIPAA

1. Does the research involve Protected Health Information (PHI) in any way?

The only PHI we will be collecting is the participant's name and phone number. This information will only be on the consenting forms which will be kept in a locked cabinet. Participant names will be in the Redcap database which is password protected.

Subjects

1. Describe in detail what will be done to identify and recruit participants?

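### Use of cortisol-altering medicines is neither an eligibility item, nor recorded, nor handled in the cortisol analysis, so a medicine-related change cannot be told from an MBRT effect

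*Combined protocol and SAP*

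**What the plan says.** **Eligibility.** The one inclusion criterion (Design, item 3) is occupational: "Be employed as a law enforcement official, firefighter, or emergency medical services technician or supervisor from Cabell, Kanawha, or Putnam Counties". The exclusions (Design, item 4) begin "Exclusionary criteria include 1) at high risk for suicide, 2) a current psychotic disorder or significant co-morbid diagnosis", continue with high scores on three screening questionnaires, and end with "4) primary substance use disorder". No medicine or endocrine condition is named.

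**Data collected.** Design, item 6b states: "The study is composed of three general sets measures that will be monitored: primary outcome measures, secondary outcome measures, and mediating measures". The items listed under those three sets are questionnaires and saliva. For saliva, Design, item 1 says: "We plan to collect approximately 2-3 ml of saliva at 0, 30, and 45 minutes after awakening in the morning at times 0,1,2, and 3". No medication item is listed for any of the four time points. The HIPAA section, item 1, says: "The only PHI we will be collecting is the participant's name and phone number".

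**Analysis.** Design, item 1 and item 6d (Aim 2 Analyses) give two cortisol analyses. The CAR mixed model has phase, time after waking and their interaction. The AUCI regression has pre-AUCI in the first step and four change scores in the second, with post-AUCI as the outcome. Neither has a medication term, a rule for setting samples aside or a sensitivity analysis.

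**Interpretation and control.** Specific aim 1 seeks improvement "compared to baseline measures and reduced stress as measured by salivary cortisol". Design, item 2 makes each participant his or her own control. Cortisol is classed as a secondary outcome (item 6b).

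**The concern.** Cortisol is the only outcome here that is not self-reported, in a study with no concurrent group, so it carries the objective part of the claim. The protocol describes it as a measure of the HPA axis. Corticosteroids act on that axis and can lower measured cortisol. This is general pharmacology, which the documents do not discuss, and I treat it as an assumption.

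Time 3 falls 90 days after the training, and some participants may start or stop such a medicine by then. A parallel control group would be expected to show similar changes; here nothing absorbs them. A start after baseline can look like a training effect, and a course that ends can mask one. In the AUCI regression, a few altered profiles could be influential points unrelated to mindfulness or stress, and so could distort the association in the second hypothesis in either direction. If use is not recorded on the day of collection, no later analysis can identify the affected samples.

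**Working it through.** **1. The plan's own figure.** Sample Size gives 2 cohorts × 35 = 70, which reproduces. Design, item 1 sets a minimum of 50. No SD, effect size or power is stated, so the sizes below rest on assumptions.

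**2. Is the gap real?** Eligibility names no medicine. The listed measures include none. The CAR model has three terms and the AUCI regression five predictors, none of them a medicine. Potential Risks, item 1 foresees that participants may need mental health care, but nothing says that new treatment is recorded. I found no other text that covers the point.

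**3. What a medicine does to AUCI.** For levels a, b, c at 0, 30 and 45 minutes, AUCI = 30(a+b)/2 + 15(b+c)/2 − 45a. Set a = 1 and let the rise be r at 30 minutes, held to 45 minutes (assumed). Then AUCI = 30r. The protocol's 50–75% rise gives 15.0 to 22.5.

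| Effect of the medicine | AUCI |
|---|---|
| None | 15.0 to 22.5 |
| All three samples halved | 7.5 to 11.25 |
| All three lowered by the same amount | 15.0 to 22.5 (unchanged) |
| Flat profile | 0 |

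So the effect on AUCI ranges from nothing to complete loss. In the third case only the phase main effect of the CAR model moves.

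**4. Size at group level.** This uses a paired pre-post test of mean AUCI as an illustration; the plan does not contain that test. Assumptions: SD equal to the mean, pre-post correlation 0.5, a net share p of participants becoming users after time 0, each losing all of the AUCI, and no true training effect. The documents give none of these inputs.

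- Standard error as a fraction of the mean: √(2(1 − 0.5)/50) = 0.141.
- Shift in standard errors: p/0.141, which is 0.28, 0.35 and 0.71 for p = 4%, 5% and 10%.
- Noncentral t with 49 degrees of freedom, two-sided 5% level:

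| p | False significant fall (nominal 2.5%) | Two-sided error (nominal 5%) |
|---|---|---|
| 4% | 4.6% | 5.9% |
| 5% | 5.3% | 6.4% |
| 10% | 10.3% | 10.7% |

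At n = 70 the standard error is √(1/70) = 0.120. For p = 5% the shift is 0.42 standard errors and the two-sided error about 7.0%.

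**5. Sensitivity to the SD.** With a normal approximation, full suppression and an SD of change from 0.75 to 1.5 times mean AUCI, two-sided error is 5.1–5.3% for 1 starter in 70, 5.7–7.7% for 3 in 70, 8.6–20% for 7 in 70 and 7.6–15.6% for 5 in 50.

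**6. Starters and stoppers together.** A simulation under the step 4 assumptions, with 2 starters and 2 stoppers among 50, gives a false-fall rate of about 2.1% against 2.5%. There is no inflation.

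**7. Not quantified.** The effect on the AUCI regression cannot be sized from the documents, because it depends on how the affected participants' change scores fall.

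**The case against.** The strongest reply is that this is a pilot, cortisol is secondary, and the net bias is small under plausible inputs. That stands, and it sets the priority. The illustration in step 4 also leans towards the worst case: it counts net starters only, with complete suppression, and tests something that neither planned cortisol analysis tests. The AUCI regression uses one pre and one post day without naming the post wave. If that wave is time 1, the window for new use is days, not months. These points limit the size of the problem; they do not supply the missing information.

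A reader might infer three stronger things that the documents do not support.

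- *That the HIPAA sentence proves no medicine is recorded.* It answers a question about PHI and goes on to say where names are kept. The study plainly collects other health data, such as PROMIS scores and cortisol. The case rests on the silence of the eligibility, measures and analysis sections.
- *That someone who starts a corticosteroid after baseline is counted as having less stress.* The plan has no classification of individuals. A starter moves a group mean or a regression fit.
- *That the bias favours MBRT.* The plan does not say which direction of CAR or AUCI change means less stress. An equal fall at all three samples leaves AUCI unchanged, and a stopped course pushes the other way.

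**Conclusion.** The omission is real: medicines that alter cortisol are absent from eligibility, data collection and analysis, and the design has no concurrent group to separate their effect from that of the training. It cannot be corrected after collection. The likely effect is modest and of uncertain sign. In the central illustration, two-sided error is about 6.4% instead of 5% (5.9% to 10.7% for 4% to 10% net new users at n = 50), and there is no inflation when starts and stops balance. The figures depend on the assumed share of users, full suppression, SD and correlation. The existence of the gap depends on none of them, only on the premise that some medicines change salivary cortisol. It affects a secondary outcome and the second hypothesis, and leaves the self-report outcomes untouched. This is a cheap improvement of minor priority.

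**What to change.** 1. At each saliva collection (times 0 to 3), add a short self-report checklist in REDCap: corticosteroid use by any route with date of last use, hormonal preparations, and recent nicotine.
2. Pre-specify that collection days with current or recent systemic or inhaled corticosteroid use are set to missing in the CAR model and the AUCI regression. Define *recent* before any cortisol result is seen.
3. Repeat both analyses with all samples as a sensitivity analysis.
4. Report hormonal and nicotine use descriptively, or in a further sensitivity analysis.

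Eligibility, training, questionnaires and the planned 70 stay as they are. The HIPAA wording needs review only if the new form requires it.

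Cost: one short form per wave, one extra analysis and a few participant-days of cortisol data lost from the main analysis. The mixed model keeps a person's other days, but in the AUCI regression a person whose pre or post day is set to missing drops out. At 5% affected that is about 0.05 × 50 = 2.5, so two or three people at the minimum enrolment.
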